## **Adverse Events of Special Interest (AESIs)**

The events of severe infections, malignancies (including non-melanoma and melanoma skin cancer, excluding carcinoma in situ of the cervix), confirmed Major Adverse Cardiac Events (MACE), and drug-related hypersensitivity reactions will be identified a priori as AESIs for summarizing in this study. Severe infections are defined as any infection meeting the regulatory definition of a SAE, or any infection requiring IV antibiotics whether or not reported as a serious event, as per the regulatory definition. Major Adverse Cardiac Events include non-fatal stroke, non-fatal myocardial infarction and cardiovascular death. All MACE events will be evaluated and adjudicated by a Clinical Adjudication Committee. The AESIs will be summarized by SOC, PT and treatment group.

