### **11.1.1.3 Adverse Events of Special Interest**

The events of severe infections (defined as any infection meeting the regulatory definition of a SAE or requiring intravenous antibiotics whether or not reported as a serious event), malignancies (including non-melanoma and melanoma skin cancer), confirmed Major Adverse Cardiovascular Events (MACE), and drug-related hypersensitivity reactions) will each be

identified a priori as an AE of special interest (AESI) for summarizing in this study. Major Adverse Cardiovascular Events include non-fatal stroke, non-fatal myocardial infarction, and cardiovascular death. All MACE events will be evaluated and adjudicated by a CAC ([Section 12.3.4](#)). An AESI must be reported as if it were an SAE ([Section 11.1.2](#))

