# Statistical Analysis Plan (SAP)

- TEAEs leading to study discontinuation
- Serious TEAEs
- TEAEs leading to death.

An overall summary for the categories above will be presented by treatment group and overall.

Due to the various durations of exposure to a treatment, the exposure-adjusted AE incidence rate (per 100 subject-years) will be summarized by treatment group. The incidence of AEs will be presented by system organ class and PT. In addition, all TEAEs will be summarized by SOC, PT and treatment group using frequency counts and percentages (i.e., number and percentage of subjects with an event).

Where a subject has the same adverse event, based on preferred terminology, reported multiple times in the study, the subject will only be counted once at the preferred terminology level in adverse event frequency tables.

Where a subject has multiple adverse events within the same system organ class in the study, the subject will only be counted once at the system organ class level in adverse event frequency tables.

When reporting adverse events by intensity, in addition to providing a summary table based on the event selection criteria detailed above, summary table will also be provided based on the most intense event - independent of relationship to study treatment.

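### The SAP tabulates AESIs only by SOC and PT, so confirmed MACE and drug-related hypersensitivity get no category count, rate or confidence bound

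*SAP*

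**What the plan says.** Protocol 11.1.1.3 names severe infections, malignancies, confirmed MACE and hypersensitivity judged drug-related, and says each is "identified a priori as an AE of special interest (AESI) for summarizing in this study". Protocol 12.2.3 lists AESIs as a safety endpoint in their own right; SAP 4.2 does not. Protocol 12.3.1 asks only for a descriptive summary.

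SAP 8.7.1 repeats the four categories. On MACE it states that "Major Adverse Cardiac Events include non-fatal stroke, non-fatal myocardial infarction and cardiovascular death", and it sends every such event to the adjudication committee. It then gives the tabulation rule: "The AESIs will be summarized by SOC, PT and treatment group". Other relevant provisions in the SAP are:

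- Section 8.7.1 counts a subject once per PT and once per SOC. It has no counting rule for an AESI category.
- The overall TEAE summary in 8.7.1 has six categories, and AESI is not one of them.
- For AEs in general, "the exposure-adjusted AE incidence rate (per 100 subject-years) will be summarized by treatment group", with incidence shown by SOC and PT.
- Section 8.1 has a general convention that two-sided 95% intervals are given where relevant. It names no method and no table.
- A separate subject-level listing of AESIs is planned.

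The malignancy definitions differ. The protocol has "malignancies (including non-melanoma and melanoma skin cancer" and stops there. The SAP has "malignancies (including non-melanoma and melanoma skin cancer, excluding carcinoma in situ of the cervix". SAP section 10 declares no change from the protocol.

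**The concern.** The current protocol's objectives are all safety objectives, and no power is calculated. What the study can contribute on rare risks is therefore an estimate with its precision: how many subjects had a confirmed MACE, over how much exposure, and how high a rate the data still allow. A table organised by SOC and PT does not answer that for a composite. Its components fall in separate rows with counts of perhaps 0 or 1. Subject counts cannot safely be added across rows, because someone with two component events is counted in each. A category with no events produces no row, although its upper confidence limit is then the main result.

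**Working it through.** The documents give no AESI rate, interval or expected count, so there is no planned figure to reproduce. The check has two parts.

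**1. What the specified table can show, by category**

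| Category | Row in a SOC/PT table restricted to AESIs |
|---|---|
| Confirmed MACE | None; stroke, infarction and cardiovascular death carry different PTs and normally more than one SOC |
| Drug-related hypersensitivity | None; terms can fall under several SOCs |
| Severe infections | Approximated by the infections SOC row |
| Malignancies | Approximated by the neoplasms SOC row |

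The SOC placements are ordinary MedDRA structure, taken here as an assumption because the documents do not reproduce the dictionary.

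**2. Size of the loss (illustration)**

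Inputs from the documents:
- At most 286 subjects (SAP 3.1).
- Exposure is last dose date minus first dose date plus 1 day (SAP 8.5.1), and the last dose is at Week 200. The maximum per subject is 200 × 7 + 1 = 1,401 days.

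Assumptions not in the documents:
- All 286 enrol.
- Mean follow-up is 100%, 75% or 50% of the maximum.
- The three starting groups are equal in size.
- The rate denominator is the 8.5.1 exposure, since SAP 8.7.1 does not define its subject-years.

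Total exposure T = 286 × 1,401 / 365.25 = 1,097 subject-years. At 75% this is 823, and at 50% it is 549.

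The exact Poisson 95% limits for x events, per 100 subject-years, are:
- lower = 100 × χ²(0.025; 2x) / 2T, set to 0 when x = 0;
- upper = 100 × χ²(0.975; 2x + 2) / 2T.

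| Follow-up | T | One event (a single PT row) | Three events (composite) | Zero events, upper limit |
|---|---|---|---|---|
| 100% | 1,097 | 0.09 (0.002–0.51) | 0.27 (0.06–0.80) | 0.34 |
| 75% | 823 | 0.12 (0.003–0.68) | 0.36 (0.08–1.07) | 0.45 |
| 50% | 549 | 0.18 (0.005–1.02) | 0.55 (0.11–1.60) | 0.67 |

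Three MACE, one of each component and in three different subjects, would show as three rows of 0.09 at full follow-up. No row would show 0.27 (0.06–0.80).

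For one starting group (T/3 = 366, 274 or 183 subject-years), the zero-event upper limit is 1.01, 1.35 or 2.02. An overall column is therefore needed as well as the group columns.

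Sensitivity to the denominator: counting 208 weeks per subject gives 286 × 208 × 7 / 365.25 = 1,140 subject-years. The composite is then 0.26 (0.05–0.77) and the zero-event limit 0.32. The conclusion is the same.

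**The case against.** Several objections have force.

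- **Infections and malignancies.** A reader might infer that the planned table gives no number for any AESI category. That goes too far. With subjects counted once per SOC in a table restricted to AESIs, the infections and neoplasms rows would come close. The gap is clear only for MACE and hypersensitivity.
- **Adjudication.** A reader might also infer that unadjudicated investigator terms would be reported as MACE. Both documents limit the AESI to confirmed events and send all MACE to the committee, and protocol 12.3.5 places endpoint definitions in its charter. What is missing is the composite row, not the adjudication.
- **Hidden events.** A reader might infer that a cluster of events would go unseen. The planned AESI listing would show every one. What it lacks is a rate with a bound.
- **Existing provisions.** SAP 8.1 allows intervals, 8.7.1 has exposure-adjusted rates, and section 9 gives an overall column by default. All of this stands, but none of it is attached to an AESI category.
- **Unseen table templates.** SAP section 9 puts these in a separate document, and they may group by category. The SAP does not commit to it.
- **No breach.** The protocol asks only for a descriptive summary, and no test or power figure depends on this. The point therefore concerns a better choice of summary, not a contradiction or a biased estimate.
- **Malignancy definition.** Protocol exclusion criterion 13 exempts in situ cervical carcinoma from the malignancy-history bar, so the SAP's exclusion has a parallel. Such a case would still appear in the general TEAE tables. The difference is minor, but it is not recorded in SAP section 10.

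**Conclusion.** The point holds in limited form and should be acted on. As written, the AESI table yields no subject count, exposure-adjusted rate or interval for confirmed MACE or drug-related hypersensitivity, only an approximation for severe infections and malignancies, and nothing for a category with zero events. At full enrolment and completion the unreported MACE quantity in the example is 0.27 per 100 subject-years (0.06–0.80), against three rows of 0.09. The unreported zero-event bound is 0.34, rising to 0.67 at 50% follow-up. The event counts are hypothetical, 286 is a ceiling, and the follow-up fractions are assumptions, so the figures show scale only. The documents do not support a claim that events would be lost, that adjudication is bypassed, or that the cervical in situ exclusion materially changes the malignancy count.

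**What to change.** In SAP 8.7.1, add one AESI table with a row for each of the four categories. The MACE row should use committee-confirmed events, with its three components shown beneath it. Each row should give:

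- number and percentage of subjects with at least one event;
- subject-years, with the denominator defined;
- rate per 100 subject-years with an exact Poisson 95% interval.

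Present it by treatment group and overall, keep a row for any category with no events, and nest the SOC/PT breakdown under each category. State the flag or search that assigns events to each category, and count each subject once per category.

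Separately, align the SAP's malignancy definition with protocol 11.1.1.3, or record and justify the cervical in situ exclusion in SAP section 10.

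The cost is one extra table from existing data and a short SAP edit. No new data collection is needed.

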## **Adverse Events of Clinical Interest (AECIs)**

An AECI is a non-serious AE or occurrence that is designated to be of special interest and must be reported to the Sponsor as though it were an SAE. The AECIs will be summarized by SOC, PT and treatment group.

The following events are considered AECIs for this study:

1. An overdose of the Sponsor's product, as defined as any dose greater than the intended protocol dose. An overdose that is not associated with clinical symptoms or abnormal

# Statistical Analysis Plan (SAP)

laboratory results is to be reported as a non-serious AECI, using the terminology "accidental or intentional overdose without adverse effect."

2. An elevated AST or ALT laboratory value that is  $\geq 3 \times$  the ULN and an elevated total bilirubin laboratory value that is  $\geq 2 \times$  ULN and, at the same time, an alkaline phosphatase laboratory value that is  $< 2 \times$  ULN, as determined by way of protocol-specified laboratory testing or unscheduled laboratory testing, is to be reported as a non-serious AECI.
3. Infections that require IV antibiotics but do not meet the definition of an SAE will be designated a closely monitored AE for this study.
4. Depression and suicidal ideation and behavior events.

In addition, a listing containing individual subject adverse event data for TEAEs leading to discontinuation from study, Serious TEAEs, TEAEs leading to death, AESIs, and ECIs will be provided separately. All AEs, including pre- and post-treatment AEs, will be presented in an individual subject data listing.

## 8.7.2 Clinical laboratory evaluations

For the purposes of summarization in both the tables and listings, all laboratory values will be presented in SI units. If a lab value is reported using a nonnumeric qualifier e.g., less than (<) a certain value, or greater than (>) a certain value, the given numeric value will be used in the summary statistics, ignoring the nonnumeric qualifier.

Clinical laboratory parameters observed values and changes from Baseline will be summarized at each scheduled visit. Unscheduled visits will not be included in the summary table, but will be displayed in the listings.

Values outside the normal range will be categorized as H (above the normal range) or L (below the normal range) based on the laboratory's reference range and these will be flagged in the listings of individual subject data.

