#### **11.1.1.10 Abnormal Laboratory Values/Vital Signs/12-Lead Electrocardiograms**

Laboratory/vital signs/12-Lead ECG abnormalities should be reported as AEs/SAEs if it is clinically significant and any of the following criteria are met:

- Result is associated with signs/symptoms,
- Requires additional diagnostic testing and/or intervention,
- Leads to discontinuation or interruption of the IMP.

Any test result determined to be an error or simple repetition of a laboratory test is not required to be reported as an AE.

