# Statistical Analysis Plan (SAP)

## 8 STATISTICAL METHODS

### 8.1 General Statistical Conventions

All statistical procedures will be completed using SAS version 9.4 or higher.

Continuous variables will be summarized using descriptive statistics, including number of subjects (n), mean, median, standard deviation (SD), minimum and maximum. One additional decimal point for mean and median and 2 additional decimal points for SD will be used.

For categorical variables, summaries will include counts of subjects and percentages. Percentages will be rounded to one decimal place.

Two-sided 95% confidence intervals (CI) will be provided when relevant.

For summary purposes, baseline will be defined as the last available value prior to the date of first IMP administration in parent study.

For reporting purpose, summary tables for efficacy variables and safety variables will be displayed by nominal visit as appropriate. Unscheduled assessments will not be included in the summary tables, but will be in data listings.

All subject data, including those derived, will be presented in individual subject data listings. Unless otherwise stated, unscheduled visit results will be included in date/time chronological order, within patient listings only. All listings will be sorted by treatment group, subject number, date/time and visit. The treatment group as well as patient's sex and age will be stated on each listing. Unless otherwise stated, data listings will be based on ASaT population.

The treatment groups will be displayed in the format below in tables:

- 200 mg Tildrakizumab q4wk
- 200 mg Tildrakizumab q12wk
- 100 mg Tildrakizumab q12wk

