## 8.7.3 Vital signs

Vital signs observed values and changes from Baseline will be summarized at each scheduled visit.

A listing of vital signs by subject will be produced.

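### No laboratory or vital-sign table counts subjects with abnormal values; those not reported as adverse events reach only the listings and by-visit summaries, which leave out unscheduled results

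*SAP*

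**What the plan says.** For laboratory data, SAP 8.7.2 states: "Clinical laboratory parameters observed values and changes from Baseline will be summarized at each scheduled visit". It then says of unscheduled results: "Unscheduled visits will not be included in the summary table, but will be displayed in the listings". Values outside the reference range are categorised H or L, and "these will be flagged in the listings of individual subject data". Protocol 12.3.1 has the same by-visit summary and the same listing-only flags.

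For vital signs, SAP 8.7.3 states: "Vital signs observed values and changes from Baseline will be summarized at each scheduled visit". It gives no out-of-range category and no threshold.

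SAP 8.1 sets the statistics for continuous variables, "including number of subjects (n), mean, median, standard deviation (SD), minimum and maximum", and a general rule: "Unscheduled assessments will not be included in the summary tables, but will be in data listings".

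Two event-reporting routes also lead to tables.

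- **Adverse events.** Protocol 11.1.1.1 includes clinically relevant laboratory and vital-sign abnormalities among treatment-emergent adverse events (TEAEs). Protocol 11.1.1.10 is narrower: "Laboratory/vital signs/12-Lead ECG abnormalities should be reported as AEs/SAEs if it is clinically significant and any of the following criteria are met". The criteria are signs or symptoms, a need for further testing or intervention, or stopping or interrupting the study drug. SAP 8.7.1 counts subjects with TEAEs by system organ class and preferred term.
- **Adverse events of clinical interest (AECIs).** One item in SAP 8.7.1 is defined by laboratory values: ALT or AST at least 3×ULN with total bilirubin at least 2×ULN and, at the same time, alkaline phosphatase below 2×ULN. This pattern, "as determined by way of protocol-specified laboratory testing or unscheduled laboratory testing, is to be reported as a non-serious AECI". AECIs are tabulated by treatment group.

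**The concern.** The objectives in Protocol 8.1 and SAP 2.1 name changes in vital signs and laboratory assessments. The study has no power calculation and SAP 8.7 plans no tests on safety data, so the descriptive tables are the result.

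By-visit summaries answer whether a group moved on average and what its most extreme value was at that visit. They do not say how many subjects became abnormal, whether those subjects were normal at baseline, or what happened between visits. Repeat tests and tests prompted by a suspected problem are often unscheduled, so the values most likely to be abnormal are the ones left out.

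The SAP already uses subject-level tables elsewhere. ECG interpretation has category counts and shift tables (8.7.5), physical examination has Normal/Abnormal incidence (8.7.4), and the C-SSRS has worst-case shift tables (8.7.6). Laboratory values and vital signs have none of these.

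**Working it through.** The plan states no figure to reproduce. The check is to trace where an abnormal value would appear, then to size what a by-visit summary can show.

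**Step 1. Where each kind of result appears under the plan**

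| Result | By-visit summary | Counted by subject | Listing |
|---|---|---|---|
| Isolated ALT or neutrophil abnormality, scheduled draw, not reported as an AE | Yes, within the summary statistics | No | Yes, flagged |
| Same, unscheduled draw | No | No | Yes, flagged |
| Combined liver pattern, scheduled or unscheduled, reported as an AECI | Scheduled values only | Yes, AECI table | Yes |
| Laboratory or vital-sign abnormality reported as a TEAE | Scheduled values only | Yes, TEAE tables | Yes |
| Abnormal blood pressure or pulse, scheduled, not reported as an AE | Yes | No | Yes, no flag rule stated |
| Same, unscheduled | No | No | Yes, no flag rule stated |

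Rows 1, 2, 5 and 6 are the gap. Rows 3 and 4 are covered, but only through event reporting, and row 4 depends on the investigator's judgement. Protocol 11.1.1.10 also says that simple repetition of a laboratory test need not be reported as an AE. The combined liver criterion requires all three conditions at once, so it does not catch an isolated transaminase rise. The AECI category is in the SAP; the special-interest list in Protocol 11.1.1.3 has no liver item.

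**Step 2. Spacing of scheduled laboratory visits**

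Protocol 9.1.3.1.1 to 9.1.3.1.3 places routine laboratory tests at Weeks 0, 20, 56, 104, 152, 200 and 208. The successive differences are 20, 36, 48, 48, 48 and 8 weeks. A result found by an unscheduled draw within one of the three 48-week gaps enters no laboratory summary.

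**Step 3. What one marked value does to a by-visit summary (illustration)**

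The following are assumptions, not figures from the documents: one subject rises from 25 to 400 U/L ALT, and the group has n subjects with data. For n, 286/3 ≈ 95 assumes three equal groups at maximum enrolment; 60 and 140 show a range.

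Shift in group mean = (400 − 25)/n = 375/n:

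- n = 60: 375/60 = 6.3 U/L
- n = 95: 375/95 = 3.9 U/L
- n = 140: 375/140 = 2.7 U/L

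At a scheduled visit, the group maximum for that visit would be at least 400, so the extreme would be visible. The table would still not show whether one subject or several were abnormal, nor their baseline status. From an unscheduled draw, the effect on the mean, and on the minimum and maximum, is 0.

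**The case against.** The strongest defence is that the plan captures abnormalities that matter clinically. Clinically relevant laboratory and vital-sign findings are TEAEs and are counted with percentages. The serious liver pattern is tabulated even when an unscheduled test detects it. By-visit tables show minimum and maximum as well as the mean. The exclusion in SAP 8.1 directly follows the sentence that tables are shown by nominal visit, so it can be read as governing by-visit tables only. The study is uncontrolled and descriptive, the SAP matches the protocol, and SAP 9 puts table templates in a separate document.

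Much of this stands, and it limits the point. A reader might infer three stronger things that the documents do not support:

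- **That no table counts any abnormal result, or that unscheduled findings are barred from every table.** The TEAE and AECI tables contradict both, and ECG and physical-examination abnormalities are counted too.
- **That only mean change is reported.** Observed values, median, SD, minimum and maximum are also planned.
- **That the 48-week gaps are themselves an analysis fault.** They are a matter of schedule, and no table can show a value that was never measured. The point concerns values that are measured.

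What the defence does not answer is the isolated abnormality that is not reported as an event. A maximum gives one value per group and visit, not a number of subjects. Reading the exclusion as by-visit only would not help by itself, because no other laboratory or vital-sign table exists for the unscheduled values to enter. Further tables may be in the separate templates, but the SAP text does not commit to them.

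**Conclusion.** The point holds in this limited form. The SAP plans no laboratory or vital-sign table that counts subjects with out-of-range or markedly abnormal values. Such results are counted only if reported as TEAEs or as the single combined liver AECI. An isolated abnormality outside those routes can go uncounted, and its peak is missing from all tables if it came from an unscheduled draw.

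How many subjects this affects cannot be estimated from the documents: neither the frequency of abnormalities nor the number of unscheduled draws is given. The ALT arithmetic is illustrative only. The conclusion rests on the SAP text without the table templates. It does not imply that safety data are lost, since every value is still listed. This is a worthwhile, inexpensive improvement to reporting on a primary objective.

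**What to change.** 1. In SAP 8.7.2, add Low/Normal/High shift tables by treatment group, from baseline to each subject's lowest and to each subject's highest post-baseline value in the extension. Use scheduled, unscheduled and EoT/Follow-up results. Use the baseline defined in SAP 8.1 (parent study), and repeat from the extension baseline defined in Protocol 12.3.
2. Add separate counts of subjects with ALT or AST at least 3×ULN, and with total bilirubin at least 2×ULN, on the same all-values basis. Both cut-offs are already in the SAP's AECI definition.
3. State in SAP 8.1 and 8.7.2 that the exclusion of unscheduled values applies only to by-visit summaries.
4. In SAP 8.7.3 and 8.7.5, show each subject's minimum and maximum post-baseline vital signs and QTcF, again using all values. The documents define no categories for these, so none is assumed here.

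The cost is SAP wording and standard programming. The data and the H/L classification already exist, and no visit, sample or clinical rule changes. The downside is a few more tables, which may look less favourable than the by-visit summaries.
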